Given the anticipated differences in patients who seek care in these settings, we propose using propensity score techniques to balance patient characteristics in the two treatment groups both within and across sites. We will use relatively new methods developed for use of propensity scores in the context of multilevel data.⁴² We look towards using propensity scores for achieving balance in the distributions of covariates to allow for a causal comparison. Our treatment assignment is at the individual level and we propose using appropriate propensity weighting methods to generate valid causal inferences, under the assumption of absence of unmeasured confounders.

For causal comparisons, we adopt the potential outcome framework for causal inference.⁴³ Under the standard stable unit treatment value assumption (SUTVA)⁴⁴, which states that the outcomes for each patient are unaffected by the treatment assignments of the other patients, each patient has two potential outcomes corresponding to the two treatments (ED or IC care), only one of which is observed for each patient. We believe the SUTVA assumption to be true in our setting. We aim to estimate the population average treatment effect, although we may also look at the *population average treatment effect on the treated (ATT)*, which we expect will be very similar.

Notation Let $k = 1, 2, \dots, K$ denote number of regions and $i=1, 2, \dots, n_k$ denote the number of participants in region k . Total sample size is $n = \sum_{k=1}^K n_k$. Each subject belongs to one of two groups, ED (control) or IC (treatment) care. Let Z_{ki} be the binary variable indicating whether the subject is in the treatment ($Z=1$) or control ($Z=0$) group. Also, let U_{ki} be a vector of subject-level covariates and V_k be a vector of region-level covariates, and $X_{ki} = (U_{ki}, V_k)$. For each subject, an outcome Y_{ki} is observed, which, in our study, can be continuous or binary. The propensity score is defined as $e(X_{ki}) = \Pr(Z_{ki}=1 | X_{ki})$.

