Fitting a Propensity Model Given the multi-region (clustered) data, we cannot use standard techniques for propensity score modeling but instead will use a *random effects model* that accounts for clustering. We have chosen this model because we are uncertain about all of the cluster-level covariates that might impact on treatment effect. The few that we hypothesize to be regional-level confounders, as described above, we will include in the model. The individual level covariates will include: SCD complications, self-reported number of acute care visits and hospitalizations in the prior 12 months, pain rating upon first arrival for care, distance from residence to site of care, and demographic variables. The random effects model to generate the propensity score is as follows:

$$\text{logit}(e_{ki}) = \delta_k + X_{ki} \beta \quad (1)$$

This model includes individual level covariates, as well as cluster-specific intercepts due to measured and unmeasured cluster-level covariates, and a prior distribution for cluster-level main effects, $\delta_k \sim N(0, \sigma_\delta^2)$. We expect that since we will have many patients within each region (cluster), we should not have any difficulty in fitting the random-effects model. The goodness of fit of this model will be checked by conventional diagnostics of covariate balance between the ED and IC treated patients, checking the overall and within-region balance of the weighted distribution of covariates in the two groups.

Estimating an Overall Treatment Effect We will then use the inverse of the propensity score, e_{ki} , generated from the random effects model described above, to *weight the outcomes* for each individual. This will allow us to draw valid inferences about the differences between groups. We propose using a non-parametric clustered-estimator as our inverse-probability-weighted estimator.

$$\hat{\pi} = \frac{\sum_{k=1}^K \hat{\pi}_k w_k}{\sum_k w_k} \quad (2)$$

Where $w_k = \sum_{i \in k} w_{ki}$, $w_{ki} = Z_{ki}/e_{ki} + (1-Z_{ki})/(1-e_{ki})$, and $\hat{\pi}_k$ is the inverse-propensity weighted treatment effect for the k -th region. This estimator accounts for clustering of the patients by region. The standard error of the estimate will be generated by bootstrapping.

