To test the first hypothesis (time to pain medication), we will use the observed time to first dose (a continuous outcome) in the two groups. We do not need to use time-to-event models since there will be no censoring. We will evaluate whether the time needs to be log-transformed in order to be approximately normally distributed. To test the second hypothesis, we will describe the proportion of patients in each group that is reassessed in the first 30 minutes after dosing. We will describe the proportion of patients admitted in each of the treatment groups, using the estimator described above. For evaluations of the difference in *patient experience* of care in these two settings this likely reflects the adequacy of symptom relief during the visit and the patient-centeredness of the visit including being treated respectfully and feeling unthreatened in the environment. The outcome of interest is an ordinal measure on a scale of 18 points that we will analyze as a continuous outcome, using the estimator above. The other surveys will be analyzed similarly.

Sensitivity analysis In our sensitivity analyses, we will stratify patients into quintiles based on their propensity scores and test for differences in the outcomes of interest between ED and IC treated patients in each quintile. These quintile-specific estimates will be reported, as well as pooled estimates from application of random effects methods.

We will also estimate propensity scores using a fixed effect model rather than a random effects model (Eq 2). We might also explore the use of a doubly robust estimator, where we would model the potential outcomes using a random effects model. The results are expected to be similar.

We will also test whether our inferences are sensitive to hidden biases from unmeasured confounders. We will estimate how strong an unmeasured confounder needs to be related to both exposure and outcome to affect the inference about difference in effect in the treatment sites. Potential unmeasured confounders might be patient-preference for site of care, or local culture or climate regarding care of patients with SCD.

a. Statistical plan including sample size justification and interim data analysis.

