We have based the needed sample size on the outcome requiring the most participants, the admission rate from the ED v. IC. We hypothesize that we will observe an ED admission rate of 50%⁹, and an IC admission rate of 27% (an absolute reduction of at least 23%). We took the following design considerations into account in estimating the sample sizes needed to detect this difference: We have a 2-arm study (IC vs. ED) with 4 clusters (sites) per arm. With a type I error of 0.05, a type II error of 0.20 (power 0.80), and an estimated intracluster correlation coefficient (ICC) of 0.02, we will require an average of 41 participants in each cluster (site) per arm. 410 participants total (205 per arm) are required to detect our hypothesized difference in admission rate. We estimate we will observe a lost-to-follow-up rate of 18% so our total required sample size is [410/(1-0.18)] = 500 participants.

b. Early stopping rules. NA

8. Risks

a. Medical risks, listing all procedures, their major and minor risks and expected frequency.

The risks from this study are minimal. The participants may become tired or bored while filling out the surveys. There is also the risk of loss of privacy. Participants can choose to not participate in this study as it is not a treatment protocol there are no alternatives.

b. Steps taken to minimize the risks. All primary data to be collected will be de-identified using a unique identifier and will be kept in a secure office in a password protected computer. The data put in REDCap will be de-identified. As REDCap is a secure website and only deidentified data will be put in it the risk of loss of privacy is minimal. Every attempt will be made to assure that all locally collected data is kept in a secure environment and that all identifiers will be removed from primary data. The spreadsheet with the identifying info linked to the unique identifier will be destroyed when the REDCap database is finalized and locked.

c. Plan for reporting unanticipated problems or study deviations. Any breach of patient confidentiality will be reported to the IRB.

- d. Legal risks such as the risks that would be associated with breach of confidentiality.NA
- e. Financial risks to the participants. NA

9. Benefits

- a. Description of the probable benefits for the participant and for society.

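### Random-effects pooling of the propensity-quintile estimates may move this sensitivity result away from the population average effect, for a reason unrelated to confounding, if the effect varies with the propensity score

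*Combined protocol and SAP*

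**What the plan says.** Section 7 (Study Statistics) names its target: "We aim to estimate the population average treatment effect". The effect among the treated is an optional extra that is expected to be very similar. Estimation is by weighting: "We will then use the inverse of the propensity score", with Eq 2 combining the regional effects by their summed weights and a bootstrap giving the standard error.

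Under the Sensitivity analysis paragraph, "we will stratify patients into quintiles based on their propensity scores", and the emergency department (ED) and IC patients are compared within each quintile. Then: "These quintile-specific estimates will be reported, as well as pooled estimates from application of random effects methods". The plan gives no pooling weights and no estimator for the between-quintile variance. It does not say what quantity the pooled value estimates, or how to read a difference from the primary result. It also does not say whether the quintiles are cut on the whole sample or within region.

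**The concern.** Propensity quintiles are slices of one population, not separate studies. If they are cut on the whole sample, each holds one fifth of the patients, so the population average effect is the plain mean of the five quintile effects. Eq 2 has the same target: each patient's weight Z/e + (1-Z)/(1-e) has expectation 2, so regions count in proportion to their patients.

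Random-effects pooling weights quintile q by 1/(v_q + tau^2), where v_q is the variance of that quintile's estimate and tau^2 is the between-quintile variance, here estimated from only five strata. Precision falls where one setting is rare, particularly where the more variable setting is rare. The IC share should differ across quintiles if the score predicts setting at all, and the plan refers to "Given the anticipated differences in patients who seek care in these settings". If the effect also differs along the score, the pooled value and the primary estimate are averages over differently weighted populations. A gap between them could be taken for a sign of confounding, or could hide one. The setting is not randomised, and this is one of the study's planned robustness checks, so its reading should be clear in advance.

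**Working it through.** The plan states no figure for the pooled quintile value, so there is nothing to reproduce. The check asks how far the two weightings can differ.

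**Inputs from the documents**
- 410 evaluable participants (section 7a), so 410/5 = 82 per quintile, taking one record per participant.
- ED time to first dose: mean 190 min, SD 129.8 (section 3), rounded to 130.
- IC time to first dose: mean 57.7 min, 95% CI 56.5 to 58.8, 3874 visits (section 3). Implied SD = (58.8 - 56.5)/3.92 × sqrt(3874) = 36.5 min, treating visits as independent.
- Difference, IC minus ED: 57.7 - 190 = about -132 min.
- Admission: 50% ED and 27% IC, difference -0.23 (section 7a).

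**Assumptions, because the documents give none**
- IC shares by quintile of 0.28/0.47/0.60/0.72/0.85 for time to first dose; other patterns are noted below.
- The effect is either constant or changes by 30 min per SD of the score covariate.
- "Random effects" means DerSimonian-Laird pooling.

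**Step 1: variances, time to first dose.** v_q = 36.5²/n_IC + 130²/n_ED, with n_IC = 82 × share and n_ED = 82 × (1 - share). First quintile: 1332/22.96 + 16900/59.04 = 58.0 + 286.2 = 344. The five values are 344, 423, 542, 759 and 1393.

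**Step 2: weights with tau^2 = 0.** Weights proportional to 1/v_q are 0.32/0.26/0.20/0.14/0.08. These are fixed-effect weights, the extreme case.

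**Step 3: constant effect of -132.** Any weights summing to 1 give -132. Simulated random-effects pooling averaged -132.1. Its SD was about 10.5 min. Equal weights have SD sqrt(344 + 423 + 542 + 759 + 1393)/5 = 58.8/5 = 11.8 min.

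**Step 4: varying effect.** With quintile means of a standard normal covariate (±1.40, ±0.53, 0) and 30 min per SD, the effects are -174/-148/-132/-116/-90, or the reverse. Their plain mean is -132.
- With tau^2 = 0 weights the pooled mean would be -143.9, a shift of 11.9 min.
- With random-effects weights, tau^2 pulls the weights toward equality. Their mean is about 0.26/0.24/0.21/0.17/0.12, and the pooled mean is -137.3 to -137.7 (reversed gradient: -126.3 to -126.6). The shift is about 5 to 6 min, roughly 4% of 132, against an SD of about 11.5 min.
- Equal weights recover -132.

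**Step 5: admission.** v_q = p1(1-p1)/n_IC + p0(1-p0)/n_ED, with p0 = 0.50.

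| IC shares | Effect by quintile | Population average | Random-effects mean |
|---|---|---|---|
| 0.05/0.10/0.20/0.40/0.70 | -0.03 to -0.43, rising in size | -0.230 | -0.275 |
| 0.05/0.20/0.50/0.80/0.95 | -0.10/-0.23/-0.40/-0.23/-0.10 | -0.212 | -0.256 |
| several patterns | constant -0.23 | -0.230 | -0.234 to -0.243 |

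Across the varying-effect patterns tried, the shift was 0.3 to 4.5 points. The constant-effect row shows a shift of 0.4 to 1.3 points that is not a change of target: it arises because the weights use estimated binomial variances. The SD of the pooled value was 0.051 to 0.081. Equal weights came within 0.1 point of the population average in every pattern, with SD 0.049 to 0.084.

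**Step 6: other patterns for time.** With wider or skewed IC shares, and an IC SD of either 36 or 129.8, the shift was 0 to 11 min against an SD of 10 to 19 min.

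**The case against.** A reader might infer that random-effects pooling simply does not estimate the population average effect. The documents do not support that. With a constant effect every weighting has the same target, and a gap needs both the IC share and the effect to vary along the score. The plan posits no such variation, and its expectation that the average effect and the effect among the treated will be very similar points mildly the other way. That is an expectation rather than a safeguard, and choosing a random-effects method itself allows for quintile effects that differ.

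A reader might also take the 0.32/0.26/0.20/0.14/0.08 weights as the plan's. They are not: they assume tau^2 = 0, whereas the distortion needs heterogeneity, and heterogeneity moves random-effects weights back toward 0.20.

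Nor does it follow that a comparison with the primary result would be impossible to interpret. Every shift in the scenarios tried was below one SD of the estimate, and none would overturn a 132-minute or 23-point difference. The five quintile estimates are reported, so a reader can average them, though without a planned standard error. The plan also has a fixed-effect propensity model and an unmeasured-confounder analysis, and may add a doubly robust estimator.

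Finally, the plan does not name the algorithm, and elsewhere in section 7 it uses the term random effects for region-level models. Standard meta-analytic pooling is the natural reading of the sentence, but it is a reading.

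These objections narrow the point without removing it. One SD of a single estimate is also a lenient yardstick, because both estimates come from the same patients. The SD of the difference between random-effects and equal-weight pooling was about 3.4 min for a shift of about 5 min, and 2.2 points for the 4.5-point shift, or roughly 1.6 and 2 SDs. That comparison is between two poolings of the quintiles, not with Eq 2 itself.

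**Conclusion.** The point holds in conditional form. If the IC share and the treatment effect both vary with the propensity score, standard random-effects pooling of the quintiles may land away from the population average effect that the plan targets, with no confounding involved. On the central assumptions the size is about 5 to 6 min on 132. For admission it is up to about 4.5 percentage points, and in some patterns part of that comes from estimated binomial variances.

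These figures rest on assumed quintile shares and effects, 82 patients per quintile, DerSimonian-Laird pooling, and quintile estimates that are each unbiased for their own quintile. The 4.5-point skewed case has an average IC share of (0.05 + 0.10 + 0.20 + 0.40 + 0.70)/5 = 0.29, which is not the equal split in the sample-size section. The symmetric pattern, which does have an equal split, still gives 4.4 points.

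The primary analysis is unaffected. This is a small specification improvement to one sensitivity summary.

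**What to change.** In the Sensitivity analysis paragraph, replace the random-effects phrase with pooling of the five quintile estimates by each quintile's share of patients (0.20 each if cut on the whole sample), and state how the quintiles are cut. Take the standard error from a bootstrap, as for Eq 2. Keep the quintile-specific estimates, since they show directly whether the effect varies. If a random-effects value is still wanted, report it beside this one and label it as a different summary that need not match the primary target.

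The cost is one phrase in the plan, a rule for bootstrap replicates in which a quintile has no patients from one setting, and at most a slightly wider interval, because sparse quintiles keep full weight. In the constant-effect example the SD is 11.8 min against about 10.5. For admission the two ranges nearly coincide (0.049 to 0.084 against 0.051 to 0.081).

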
A similar clinic to the SCIC opened at Froedtert Hospital in Milwaukee (FASCC) in 2011. The FASCC clinic is open weekdays and serves the needs of 300 adults with SCD. The average length of stay in the clinic is 3 hours and 96.5% of visits end with the patient being discharged home. Since this clinic opened there has been a 38% decrease in admissions and a decrease in 30 day readmissions from 61 to 28%.

Without a direct comparison of ED to IC, many argue that there is something different about the patients that receive care in an ED versus those that seek care in an IC. Further, the recent expansion in ICs has been driven primarily by economic consideration (length of stay, readmissions), rather than by patient-centered outcomes, on which there is a lack of data. Demonstrating attainment of important clinical outcomes in ICs may increase their stability and viability. **With this proposal we will demonstrate that the improved outcomes seen in an IC v. the ED are not due to differences in the type of patients seen for care but rather in the processes of care for VOC in these two sites.**

4. Study Procedures

- a. Study design, including the sequence and timing of study procedures (distinguish research procedures from those that are part of routine care).

We will prospectively enroll patients that are seen in participating centers into a study cohort. We will then capture data from their acute visits. We will enroll participants from 4 sites: Baltimore, Cleveland, Milwaukee and Baton Rouge. When any participant is treated in either an ED or IC, data on clinical outcomes and patient experiences of care will be collected.

Baseline data collection will include: SCD genotypes and co-morbidities³⁵

- a. AVN
- b. Gall bladder disease
- c. Sickle chronic lung disease
- d. Leg ulcer
- e. Priapism (male)
- f. Renal failure
- g. Retinopathy
- h. Stroke

2. Self-reported number of acute care visits and hospitalizations in the prior 12 months
3. Daily chronic pain using the Numeric Rating scale (NRS).
4. Prior and current treatments, including:
 - a. hydroxyurea use
 - b. chronic transfusions
 - c. pain medications, (specific regimens used to treat chronic daily or intermittent pain)

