After participants have consented they will be asked to contact by phone or email the research assistants about all acute care visits. In addition, the research assistant will review the daily census for IC's and ED's at the local site to identify participants with an acute care visit. Furthermore, each participant will be contacted by phone monthly and asked about acute care visits.

Once an acute care visit for an uncomplicated VOC has occurred, the following data will be collected: Time crisis started, Arrival time, Triage time, Pain level on arrival, Time to first dose of opioid, Time from first dose to nurse reassessment of pain, Time in the ED/IC, Pain level at discharge from ED/IC, Change in pain scale from arrival to discharge, Disposition at time of discharge from ED/IC (home, admit, etc.). In order to assess patient experiences of care in the acute setting, participants will be surveyed either toward the end of their acute visit or by phone within 72 hours of their visit. As reinforcement, at each monthly call, we will verify contact information and encourage participants to call us within 3 days of any acute visit. The survey tools that will be used include the Painful Crises Experiences of Care for SCD tool (PEPS); a survey of safety and a survey of patient satisfaction with ED pain management.

- b. Study duration and number of study visits required of research participants. Participants will be part of the study for 18 months. During which time there will be no in person study visits. There will be monthly phone calls and contact at the time of acute care visits.
- c. Blinding, including justification for blinding or not blinding the trial, if applicable. NA
- d. Justification of why participants will not receive routine care or will have current therapy stopped. NA
- e. Justification for inclusion of a placebo or non-treatment group. NA
- f. Definition of treatment failure or participant removal criteria. NA
- g. Description of what happens to participants receiving therapy when study ends or if a participant's participation in the study ends prematurely. NA

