There will be no direct benefit to the subjects for participating in this study. What is learned from this study may improve the way in which adults with VOC are treated in the future.

Importance of the Knowledge to be Gained The knowledge gained from this first time comparison of the treatment of acute pain in SCD comparing ED's and IC's will result in a better understanding of where this treatment should occur. The study will demonstrate how IC's can provide more rapid and appropriate care for this patient population and this should lead to greater access to these services for patients throughout the US who suffer from SCD.

10. Payment and Remuneration

- a. Detail compensation for participants including possible total compensation, proposed bonus, and any proposed reductions or penalties for not completing the protocol.

We will compensate participants for time and inconvenience associated with study participation. Participants will receive \$25 for completing the initial study survey, and \$25 every 6 months thereafter (for a total of 18 months of follow-up), for maintaining ongoing participation and communication with the study.

11. Costs

- a. Detail costs of study procedure(s) or drug (s) or substance(s) to participants and identify who will pay for them.

NA

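### Patient preference for site of care is named as a potential unmeasured confounder, yet no listed item records it; one question added to the initial survey would partly capture it.

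*Combined protocol and SAP*

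**What the plan says.** Section 7 (Study Statistics) offers the propensity-weighted comparison as causal "under the assumption of absence of unmeasured confounders". The sensitivity-analysis paragraph of the same section adds: "Potential unmeasured confounders might be patient-preference for site of care, or local culture or climate regarding care of patients with SCD". The handling it plans is an estimate of how closely a hidden variable would have to be tied to both setting and outcome before the inference changed.

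The lists of data to be collected or modelled are these:

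- Section 4a, clinical baseline: "Baseline data collection will include: SCD genotypes and co-morbidities", followed by a list of complications.
- Section 4a, other baseline: "Self-reported number of acute care visits and hospitalizations in the prior 12 months", then daily chronic pain and treatments.
- Section 7, Fitting a Propensity Model: SCD complications, prior acute visits and hospitalizations, and "pain rating upon first arrival for care, distance from residence to site of care, and demographic variables".
- Section 4a, visit surveys: an experience-of-care tool, "a survey of safety and a survey of patient satisfaction with ED pain management", given late in the visit or by phone within 72 hours.

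Section 10 pays participants for "completing the initial study survey", so a baseline contact already exists. Section 3 gives the motive for the study: "many argue that there is something different about the patients that receive care in an ED versus those that seek care in an IC". It then undertakes to show that better IC results come from the process of care and not from the type of patient.

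**The concern.** The study is not randomized, and patients have some choice of where to seek care. A patient's prior view of the two settings is one form of the selection argument that section 3 sets out to answer. If that view affects both the choice of setting and the result, weighting on the listed covariates leaves part of it in the estimate.

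This is most plausible for the experience, satisfaction and safety surveys. Section 7 itself says that the experience score reflects being treated with respect and not feeling threatened, and a patient's earlier opinion of a setting could color such ratings. It is less obvious for time to first parenteral dose (the primary outcome), admission, or reassessment at 30 minutes.

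Preference before exposure has to be asked before exposure. If the question is left out at enrollment, later analysis cannot recover the answer.

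**Working it through.** **1. Is preference recorded anywhere?** Reading the lists against each other:

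- No baseline item in section 4a is a preference item. The prior-visit count is not split by ED and IC, so it is not a proxy.
- No propensity covariate in section 7 is preference. Distance to the site may track choice in part, but it measures access.
- The region intercepts can absorb some of the other example the plan gives, local culture. They cannot absorb differences between patients within a region.
- The visit surveys come at the end of the exposure or after it, so they cannot serve as pre-exposure covariates.

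The content of the initial survey is not shown, and the section 4a list is not exhaustive (distance and demographics enter the model but are absent from it). What can be said is that no listed item records preference, and that section 7 treats it as unmeasured.

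**2. How large could the bias be on the experience score?** The plan gives no figure to reproduce. All inputs except the 18-point scale (section 7) are assumptions: half of patients prefer the IC, half of visits are to the IC, preference multiplies the odds of IC use by OR = 2, 4 or 6, and IC-preferrers score 1 to 3 points higher in both settings.

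With both margins at one half, P(prefers IC | treated in IC) = √OR / (1 + √OR), and the corresponding share in the ED is one minus that. The crude bias is the imbalance multiplied by the score shift.

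| OR | Prefer IC, among IC-treated | Prefer IC, among ED-treated | Imbalance | Bias at 1 point | Bias at 3 points |
|---|---|---|---|---|---|
| 2 | 0.586 | 0.414 | 0.17 | 0.17 | 0.51 |
| 4 | 0.667 | 0.333 | 0.33 | 0.33 | 1.00 |
| 6 | 0.710 | 0.290 | 0.42 | 0.42 | 1.26 |

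The range is about 0.2 to 1.3 points toward the IC. This is before weighting on the planned covariates; only the part of preference that they do not explain would remain.

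**3. Does the direction hold?** Not in general.

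- Suppose patients score d points higher wherever they get their preferred site. At OR 4, 66.7% of patients in each setting are at their preferred site, so both means rise by 0.667d and the crude difference is unchanged. The true average effect is also unchanged: it is d higher for the half who prefer the IC and d lower for the other half. The bias is zero.
- Suppose IC-preferrers are harsher raters by 1 to 3 points in both settings. The table then changes sign, and the bias runs against the IC.

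**4. Admission, for scale only.** Section 7a plans on 50% in the ED and 27% in the IC, a difference of 23 points. If the prevalence of preference differs by 20 to 60 points between settings and preference changes admission risk by 5 to 20 points (both assumed), the bias is 0.20 × 0.05 = 1 point to 0.60 × 0.20 = 12 points, or 4% to 52% of 23, in either direction. The planned risk ratio is 0.50/0.27 = 1.85, so the E-value is 1.85 + √(1.85 × 0.85) ≈ 3.1. A confounder of moderate strength could distort an effect of that size but would probably not remove it.

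**5. What does adjustment cost in the weights?** In the symmetric case an IC-preferrer treated in the ED has weight 1 + √OR from preference alone: 2.4 at OR 2 and 3.4 at OR 6, against 2 if preference did not matter. Stronger preference would push weights higher and strain overlap.

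**The case against.** The strongest reply is that the plan already deals with the issue openly. It states the assumption, gives preference as an example of how it might fail, and commits to a standard hidden-bias analysis. It also adjusts for distance, prior use, arrival pain and demographics, some of which may track choice of setting. This stands: the plan does not ignore the problem, and measuring preference is an improvement rather than the correction of an error. What the hidden-bias analysis cannot do is say whether preference reaches the strength that it finds would be needed.

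A second reply is that preference may predict setting without affecting time to first dose. It would then act like an instrument, and adjusting for it would mainly widen the interval. That also stands, and no specific case has been made for admission or reassessment. For those outcomes adjustment belongs in a sensitivity analysis.

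A third is that one answer at enrollment is a limited measure. Follow-up lasts 18 months and preference can change. Setting also depends on access: section 3 describes the Milwaukee clinic as open on weekdays. This limits what the item can achieve; it does not make the item useless.

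A reader might go further and infer that the plan concedes preference as a likely or leading violation. It does not. The wording is tentative, preference is not ranked above local culture, and the section 3 remark about different patients does not mention preference.

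**Conclusion.** The point holds as a cheap improvement, chiefly for the experience, satisfaction and safety surveys. The causal comparison assumes no unmeasured confounders, the plan names preference as a potential one, and no listed item records it although a paid initial survey offers a place to ask.

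The size is unknown. The 0.2 to 1.3 points rest wholly on the assumed preference split, even use of the settings, odds ratios and score shifts, and they are crude figures. A reader might infer that the results will be biased toward the IC, or that the primary comparison is invalid. The documents support neither: they hold no data on preference, the sign depends on how preference acts on ratings, and a link between preference and time to first dose is not established.

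**What to change.** - Add one question on preferred site of acute care to the initial survey, asked before any study visit.
- For the experience, satisfaction and safety surveys, report the weighted estimate with preference added to the propensity model beside the estimate from the planned model. Check overlap and extreme weights for both.
- Use the observed associations of preference with setting and with outcome to benchmark the planned hidden-bias analysis.
- For time to first dose, admission and reassessment, report the preference-adjusted result as a sensitivity analysis only.
- State in section 7 that a single enrollment answer reduces this confounding and does not remove it.

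The cost is one survey item and one more analysis, with possibly wider intervals in the adjusted results. No extra visit or procedure is needed.
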